8.3.1.1. Progression of cholangiocarcinoma

Progression of cholangiocarcinoma should not be reported as an AE if it is clearly consistent with the suspected progression of the underlying cancer as defined by RECIST v1.1 ([Appendix 3](#)). Clinical symptoms of progression may be reported as AEs if the symptoms cannot be determined as exclusively due to the progression of the subject's underlying cholangiocarcinoma or does not fit the expected pattern of progression for the disease. If there is any uncertainty about an AE being due only to the disease under study, it should be reported as an AE or SAE.

8.3.1.2. Preexisting medical conditions

A preexisting medical condition is one that is present at the Screening Visit for this study. Such conditions should be recorded on the Medical History eCRF. A preexisting medical condition should be recorded as an AE only if the frequency, severity, or character of the condition worsens during the study. When recording such events on the Adverse

Event eCRF, it is important to convey the concept that the preexisting condition has changed by including applicable descriptors (eg, "more frequent headaches").

8.4. Definition of serious adverse events

Any adverse event that at, any dose:

- results in death,
- is life-threatening⁽¹⁾,
- requires inpatient hospitalization or prolongation of existing hospitalization,
- is medically significant⁽²⁾,
- results in persistent or significant disability/incapacity⁽³⁾,
- is a congenital anomaly/birth defect⁽⁴⁾.

⁽¹⁾ Life-threatening in this context refers to an event in which the participant was at risk of death at the time of the event; it does not refer to an event which hypothetically might have caused death if it were more severe.

⁽²⁾ Any event that might not be immediately life-threatening or result in death or hospitalisation but might jeopardise the participant or might require intervention to prevent one of these outcomes (for example: oedema or allergic bronchospasm that required intensive treatment at home, blood dyscrasias, convulsions that do not result in hospitalisation, or development of drug dependence or drug abuse). The Investigator should exercise his/her scientific and medical judgement to decide whether or not such an event requires expedited reporting to Sponsor.

⁽³⁾ Disability/incapacity in this context refers to any event that seriously disrupts the ability of the participant to lead a normal life, in other words leads to a persistent or permanent significant change, deterioration, injury or perturbation of the participant's body functions or structure, physical activity and/or quality of life.

⁽⁴⁾ Congenital anomaly or birth defect refers to the exposure to the IMP before conception (in men or women) or during pregnancy that resulted in an adverse outcome in the child.

8.5. Definition of overdose

This refers to any intake of a quantity of IMP or a product other than the IMP taken as part of the protocol which is above the maximum dose recommended in the study protocol, independently of the occurrence of any AE.

The quantity should be considered per administration or cumulatively regarding the maximum dose recommended in the study protocol.

An overdose or incorrect administration of study treatment is not an AE unless it results in untoward medical effects.

Any study treatment overdose or incorrect administration of study treatment should be noted on the Study Drug Administration eCRF.

8.6. Definition of adverse event of special interest

An adverse event of special interest (AEOSI) is one of scientific and medical interest or concern regarding the IMP for which recording rules, special documentation such as hospital records and/or adjudication committee could be appropriate. It may be a serious or non-serious AE that may require further investigation in order to be characterized and understood.

AEOSI include:

Any QT prolongation event assessed as Grade 2 or worse (e.g., QTcF interval longer than 480 msec or any QTcF interval variation that is equal or more than 60 msec than the reading at baseline) with Torsade de pointes or polymorphic ventricular tachycardia or signs/symptoms of serious arrhythmia, irrespective of the seriousness of the event, should be reported as an AEOSI to the Sponsor within 24 hours. See [Section 8.11.1](#) for further details on managing subjects with QTcF Prolongation. See [Appendix 8](#) for Fridericia's formula.

8.7. Classification of an adverse event (seriousness, severity, causality, expectedness)

It is important that the Investigator gives his/her own opinion regarding the **seriousness**, the **intensity** of the event as well as the **cause-effect relationship** between an adverse event and the research or disease progression. This evaluation must be assessed by the Investigator and reported in the AE form. In addition, the Sponsor will be responsible for the evaluation the **expectedness** of the event (see [Section 8.8.2](#)).

The Seriousness should be evaluated according to international guidance (see definition [Section 8.4](#)). It is under Investigator's responsibility to evaluate the AE seriousness according to international guidance (see ICH Topic E2A and EU DIRECTIVE 2001/20/EC of 4 April 2001 or further regulation (EU) No 536/2014). The Sponsor will review the AE seriousness. The seriousness may be upgraded (but never downgraded).

The severity of all AEs will be graded according to the NCI-CTCAE on a five-point scale (Grade 1 to 5):

- Grade 1: Mild; asymptomatic or mild symptoms; clinical or diagnostic observations only; intervention not indicated.
- Grade 2: Moderate; minimal, local or non-invasive intervention indicated; limiting age-appropriate instrumental ADL¹.
- Grade 3: Severe or medically significant but not immediately life-threatening; hospitalization or prolongation of hospitalization indicated; disabling; limiting self-care ADL².
- Grade 4: Life-threatening consequences; urgent intervention indicated.
- Grade 5: Death related to AE.

The cause-effect relationship

The Investigator must make an assessment in the AE form whether the AE is related or not to the research, meaning:

- a procedure scheduled in the study protocol (i.e. exercise test, MRI, etc.), or
- a change or withdrawal of previous / concomitant treatment related to the conditions of the protocol or
- a product other than the IMP, taken as part of the protocol;

Moreover, the Investigator has to assess if the AE is related to disease progression. Cases ticked “related” by the Investigator or judged by the Sponsor as having a reasonable suspected causal relationship to the IMP (AE linked to the MoA of the IMP...), will be considered as suspected Adverse Drug Reaction. In general, if a relationship between AE and IMP is at least reasonably possible (i.e. the relationship cannot be ruled out) it is to be considered as “related”.

If in the Investigator’s opinion there is a causal relationship with the IMP, the AE must be considered as related to study protocol.

8.8. Reporting procedures

8.8.1. Time frame for AE reporting

- Any event meeting the above mentioned definitions (see [Sections 8.3](#) and [8.6](#)) must be reported to the Sponsor on an adverse event form if it occurred from the date the participant signs the information and consent form and: After informed consent has been obtained but prior to administration of the first IMP, only SAEs caused by a protocol-mandated intervention should be reported (eg, SAEs related to invasive study procedures such as biopsies).
- At any time after the first administration of IMP up to the participant’s last IMPs administration for all events regardless of attribution
- After the participant’s last IMP administration:
 - At least 28 days but no more than 33 days after the participant’s last IMPs administration for all AEs, regardless of the supposed role of the research.
 - Irrespective of the time of onset in case of serious AE related to the research.

[figure not shown]
¹ Instrumental Activities of Daily Living (ADL) refer to preparing meals, shopping for groceries or clothes, using the telephone, managing money, etc.

² Self-care ADL refer to bathing, dressing and undressing, feeding self, using the toilet, taking medications, and not bedridden”.

Of note, events occurring between the signature of the ICF and the first administration of the IMP for which the Investigator does not consider an association with the research must be reported **as medical history or as signs or symptoms related to the studied disease** in the dedicated form of the e-CRF.

Fatal events, related or not to the research, occurring after ICF signature and before first IMP administration, must be reported on AE form.

Figure (8.8.1) 1 - Rules for Adverse Event reporting

8.8.1.1. Documentation of the event

The Investigator must ensure that all events are well documented. He/She should provide anonymized copies of relevant source documents and additional documents, if requested by the sponsor.

8.8.1.2. Follow-up of adverse events

The Investigator must ensure that follow-up of the participant is appropriate to the nature of the event, and that it continues until resolution if deemed necessary.

Any change in terms of diagnosis, severity (improvement) intensity, seriousness, measures taken, causality or outcome regarding an AE already reported must be written up in a new complete evaluation of the event documented on the “Adverse event” page previously created for the event.

In case of worsening of severity, a new complete evaluation of the event must be documented on a new “Adverse event” form.

If the AE has not resolved at the participant's final visit, the participant must be followed up suitably and any information on the outcome of the event will be noted on the “Adverse Event” form previously created for the event.

If the follow-up of the participant is not done by the Investigator him/herself (hospitalisation, followed by a specialist or the participant's general practitioner, ...), the Investigator will do everything to establish/maintain contact with the person/department in charge of follow-up of the participant.

8.8.1.3. Special situations (pregnancy, overdoses, intake of IMP by a person around the participant)

Pregnancy

If a female participant in the study becomes pregnant, the Investigator must:

- stop immediately the study treatment,
- report it on the specific eCRF pregnancy form and notify the Sponsor immediately (i.e. without delay and within 24 hours of awareness at the latest),
- Pregnancy should not be reported as AE except in the following circumstances:
 - o If it is associated with an AE. This consequence itself should be reported as an AE.
 - o While pregnancy itself is not considered to be an AE, any pregnancy complication or elective termination of a pregnancy for medical reasons will be reported as an AE. Abnormal pregnancy outcomes (e.g. spontaneous abortion, death, stillbirth, congenital anomalies, ectopic pregnancy) are considered SAEs and will be reported as such.
- contribute to the follow-up of this pregnancy and provide the Sponsor with information concerning this follow-up (notably using the 2nd page of the specific paper pregnancy form).
- If the partner of a participant becomes pregnant during the study, the pregnancy should not be reported in the e-CRF. The Investigator should **immediately** contact the Sponsor (contact details provided in the Investigator's study file) who will inform him/her about the procedure to be followed.

Overdose of IMP

- In case of overdose, the Investigator should report it on the IMP administration page). Overdose should not be reported as AE except in the following circumstances:
 - o The overdose is associated with an AE. This consequence itself should be reported as an AE.
 - o The overdose is intentional with possible suicidal/self-harming intent should be reported as an AE regardless of sequelae.
- Overdose should be followed-up to ensure that the information is as complete as possible with regards to:
 - dose details (number of units, duration, etc.) and, if multiple overdoses, details regarding other medicinal products or substance,
 - context of occurrence, i.e., intentional (suicide attempt, other reason) or accidental (error in prescription, administration, dispensing, dosage),
 - related signs and symptoms (“No related adverse events” to be reported otherwise),

- outcome.
- Insofar as possible, a blood sample should be collected for assay of the IMP taken.

Intake of IMP or occupational exposure by a person around the participant

This event should not be reported in the e-CRF. The Investigator should immediately contact the Sponsor (contact details provided in the Investigator's study file) who will inform him/her about the procedure to be followed.

8.8.1.4. Recording Methods in the e-CRF

Adverse events must be documented on the "Adverse Event" form of the e-CRF.

In case of chronic disease:

- if the disease is known when the participant enters in the study, only worsening (increased frequency and/or intensity of the episodes/attacks) will be documented as an adverse event,
- On the other hand, for the following diseases, any episode will be documented as an adverse event.
- if a disease is detected during the study and if repeated episodes enable diagnosis of a chronic disease, the episodes will be grouped on the "Adverse Event" form previously created for the event which will clearly describe the diagnosis.

8.8.1.5. Procedure for an event requiring an immediate notification

In case of an event requiring an immediate notification, the Investigator must:

- **Immediately** after being informed of this event, **fill in the participant's medical file** as well as the "Adverse Event" form of the e-CRF (for SAE, and events of special interest if applicable) according to the general instructions available in the e-CRF, without waiting for the results of the clinical outcome or of additional investigations. When data will be submitted into the eCRF, an e-mail will be immediately and automatically sent to the Sponsor. However, for special situations requiring an immediate notification the completion of the "Adverse Event" form should not be performed systematically.
- If requested by the Sponsor (person designated in the contact details provided in the Investigator's study file), provide with anonymized the documents which provide additional useful information,
- Fulfil his/her regulatory obligations to the Competent Authorities and/or to the IRB/IEC, in accordance with local regulations.

Moreover, on request, the Investigator should provide the Sponsor with the documents required in [8.8.1.1](#).

If an adverse event initially non-serious worsens and becomes a serious adverse event, this must be reported **immediately** on an "Adverse event" form of the e-CRF.

In case the e-CRF is unavailable when the Investigator was informed of an adverse event to be notified immediately he/she should:

- **Immediately** fill in a paper "Adverse event" page:
 - For serious event on a paper "Adverse event – Initial information" page,
 - For event initially non-serious on a paper "Adverse event – Initial information" page, and the worsening leading to seriousness on a paper "Adverse event – Additional information" page,

- Immediately send the page(s) by fax or a scan of them by e-mail to the person(s) designated in the contact details provided in the Investigator's study file or outside working hours, the 24-hour phone line.
 - Immediately send them by fax (contact number will be provided on a separate document)
- As soon as the e-CRF becomes available, the Investigator should enter these data in the "Adverse Event" form of the e-CRF.
- A co-Investigator designated by the Investigator can cover the above mentioned role of the Investigator when the Investigator is absent. In such a case, the Investigator must confirm what have been reported by the designated co-Investigator and inform the Sponsor parties and the head of the study centre of his/her confirmation as soon as he/she has become available.

8.8.2. Responsibilities of the Sponsor

For any AE and special situation mentioned above the Investigator must:

- **Note in the participant's medical file** the date on which he/she learned of the event (at a follow-up visit or a telephone contact with the participant or a third person, ...) and any other relevant information which he/she has learned of the event.
- **Assess** the event in terms of seriousness, severity and causality.
- **Report the event to the Sponsor** using the AE form
- **Document** the event with additional useful information.
- Ensure the **follow-up** of the event.
- **Fulfil his/her regulatory obligations** to the Competent Authorities and/or to the IRB/IEC, in accordance with local regulations.
- **Ensure the oversight on data reported** and ensure the whole content's accuracy, completeness and legibility in accordance with the GCP. The Investigator or authorised member for sign-off must confirm the authenticity of the data recorded in the e-CRF by signing-off the e-CRF in a timely manner as defined in the e-CRF guide.

Moreover, the Investigator must report to the Sponsor and/or to the IRB/IEC and/or to the Competent Authorities in accordance with the local regulation, any new information that might materially influence the benefit-risk assessment of the IMP or that would be sufficient to consider changes in the IMP administration or in the overall conduct of the clinical investigation.

In accordance with international guidance, the assessment of the seriousness and the causality of adverse events are usually made by the Investigator but falls also under Sponsor's duties, who is responsible for ensuring that all suspected unexpected serious adverse reactions are reported to Competent Authorities and Ethics Committees.

The Sponsor will review the seriousness of the adverse events and the causality of (at least) the serious adverse events, whether reported by the Investigator or upgraded by the Sponsor. The causality and the seriousness may be upgraded (but never downgraded). Anonymized copies of documents providing useful information such as reports of further consultations, laboratory tests reports, reports of other examination aiding diagnosis may be asked for the event assessment. If the assessments of the Investigator and the Sponsor are different, both will be reported in the clinical study report (CSR).

In addition, the Sponsor is responsible for determining whether an AE is **expected or unexpected**. An AE will be considered unexpected if the nature, severity, or frequency of the event is not consistent with the risk information previously described for the IMP.

Independently of the regulatory obligations of the Investigator, the Sponsor must report the pharmacovigilance data and any new safety finding likely to affect the benefit /risk balance of the product, required in ICH Good Clinical Practice guidelines and local regulations, to the appropriate Authorities, to all the Investigators involved and to the trial participants involved - through the Investigators - as mentioned in [Section 13.4](#) "Modification of the information and consent form".

8.9. Responsibilities of Data Monitoring Committee

Not applicable.

8.10. Management of treatment dose adaptations due to toxicities

Study Treatment Dose Modification and Stopping Criteria

8.10.1.1. Dose Modifications and Delays

For any AE, including AEs not specifically mentioned in [Table \(8.10.1.1\) 1](#), the Investigator may decide to delay dosing or modify the dose of ivosidenib based on clinical judgment. These decisions should be discussed with the Sponsor prior to implementation. Dose modifications of ivosidenib from 500 mg to 250 mg will be permitted on study for management of AEs ([Table \(8.10.1.1\) 1](#)). If more than one AE occurs that would require a dose modification, upon resolution of all AEs to baseline or Grade 1, ivosidenib should be dose reduced to 250 mg. Re-escalation may be allowed with approval from the Sponsor.

Dose delays are discouraged, except as needed for management of AEs, dose holds during palliative radiotherapy, and washout from palliative radiotherapy. Dose delays up to 28 days will be permitted at the discretion of the Investigator in consultation with the Sponsor for reasons including management of AEs and for mitigating circumstances (e.g., planned procedures). Palliative radiotherapy delivered in the setting of continuation of ivosidenib beyond disease progression will require a 2-week washout period after radiotherapy before the resumption of ivosidenib treatment (see [Section 8.10.1.3](#)). Palliative biliary decompression procedures will be permitted on study and will not require interruption of ivosidenib.

If the subject cannot resume ivosidenib within 28 days, the subject should be discontinued from study medication. Exemptions may be considered for those subjects who are determined by the Investigator to have received clinical benefit from treatment. Other reasons for treatment termination are provided in [Section 6.5](#). If ivosidenib is discontinued, the subject will complete the EOT and Follow-up Visits, and then enter PFS follow-up (if disease has not progressed) and survival follow-up.

If a dose is delayed for the management of an AE, the subject should resume the study at the next planned visit within a dosing cycle (eg, if the subject did not start dosing at C3D1 due to management of an AE, then dosing would be resumed at C3D1 upon resolution of the AE, not C3D15).

Table (8.10.1.1) 1 - Management of Adverse Events

Adverse Events	Action

8.10.1.2. Continuation of Treatment Beyond Radiographic Progression

In the event of radiographic progression per RECIST v1.1 but in the absence of clinical deterioration, worsening ECOG performance status, or disease progression that may compromise organ function, the subject may continue to receive study treatment with ivosidenib at the discretion of the treating physician in consultation with the Sponsor. If there is clinical deterioration or continued radiographic progression documented on subsequent imaging, treatment will be discontinued, and the subject will complete the EOT and Follow-up Visits and enter survival follow-up.

8.10.1.3. Palliative Radiotherapy After Disease Progression

Palliative radiotherapy to treat symptomatic pre-existing or new non-target lesions (per RECIST v1.1) that cannot otherwise be medically managed will be permitted after disease progression has been confirmed. Ivosidenib should be held for the duration of palliative radiotherapy. A 2-week washout from completion of radiotherapy will be required prior to starting or resuming ivosidenib. For subjects permitted to continue on ivosidenib beyond documented radiographic progression, a new baseline imaging assessment will not be required, and the imaging assessments will continue on the current schedule. All decisions to pursue palliative radiotherapy will require the Sponsor approval.

8.10.1.4. Biliary Tract Obstruction During Treatment

In the event of the development of obstructive jaundice due to biliary tract obstruction, the appropriate measures will be taken to diagnose and relieve the obstruction. Study treatment interruption is not required but will be permitted at the discretion of the Investigator.

8.11. Potential Risks

8.11.1. Guidelines for Management of QT Prolongation

The discussion of the emergency management of Torsades de pointes and its hemodynamic consequences is beyond the scope of this guideline.

Events of QTcF prolongation as defined in [Section 8.6](#) should be reported as AEs of special interest (AESIs) to the Sponsor within 24 hours, according to expedited reporting procedures.

The following are guidelines for the management of AEs of special interest based on the ivosidenib non-clinical and clinical safety findings in subjects with solid tumors to date.

Prolongation of QTcF interval has been observed in monkeys at relatively high doses of ivosidenib and has been identified as an expected risk of treatment with ivosidenib (see the Investigator's Brochure).

Subjects may be at increased risk for the development of QT prolongation when treated with ivosidenib in combination with fluoroquinolones, azole antifungal agents, or serotonin (5-HT₃) antagonists. Investigators need to be vigilant; refrain from administering concomitant medications associated with QT prolongation and if no other therapeutic options are available, monitor subjects receiving study treatment with the combination of these drugs, and evaluate ECG and electrolytes (including potassium, magnesium, and total calcium) particularly in subjects presenting with nausea, vomiting, or diarrhea. Systemic administration of a moderate or strong CYP3A4 inhibitor requires careful monitoring of QTcF.

Subjects who experience prolongation of the QTcF interval to > 480 msec (CTCAE Grade ≥ 2) while receiving study treatment, should be promptly evaluated for causality of the QTcF prolongation and managed according to the following guidelines and [Table \(8.11.1\) 1](#):

- Levels of electrolytes (potassium, total calcium, and magnesium) should be checked, and supplementation given to correct any values outside the normal range.
- Concomitant therapies should be reviewed and adjusted as appropriate for medications with known QT prolonging effects.
- If no other cause is identified and the Investigator believes it is appropriate, particularly if QTcF remains elevated (after above measures have been implemented, or as determined by the Investigator), study treatment may be interrupted, and an ECG should be rechecked in approximately 1 week after the QTcF prolongation was first observed or more frequently as clinically indicated. If QTcF has recovered or improved and the Investigator believes it is safe to do so, re-challenge with study treatment should be considered if held.
- ECGs should be conducted at least weekly (eg, at every scheduled visit) for 2 weeks following QTcF reduction ≤ 480 msec.

Table (8.11.1) 1 - Management of QT Prolongation by CTCAE Grade

NCI CTCAE Grade	Management
Grade 2: QTc interval greater than 480 msec to 500 msec*	
 Monitor and supplement electrolyte levels as clinically indicated Review and adjust concomitant medications with known QTc interval-prolonging effects Interrupt ivosidenib Restart ivosidenib at 500 mg once daily after the QTc interval returns to less than or equal to 480 msec. Monitor ECGs should be conducted at least weekly for 2 weeks following resolution of QTc prolongation.
Grade 3: QTc interval greater than 500 msec*	
 Monitor and supplement electrolyte levels as clinically indicated Review and adjust concomitant medications with known QTc interval-prolonging effects. Interrupt ivosidenib. Resume ivosidenib at a reduced dose of 250 mg once daily when QTc interval returns to within 30 msec of baseline or less than or equal to 480 msec. Monitor ECGs at least weekly for 2 weeks following resolution of QTc prolongation. Consider re-escalating the dose of ivosidenib to 500 mg daily if an alternative etiology for QTc prolongation can be identified.
Grade 4: QTc interval prolongation with signs/symptoms of life-threatening arrhythmia	
 Discontinue ivosidenib permanently.

*Increase of 60 msec or more from baseline, without value of QTc interval greater than 480 msec as per table above does not link to IMP dose interruption or reduction.

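### Protocol 8.11.1: the third bullet on QTcF above 480 msec conflicts with Table (8.11.1) 1 on interruption and on the restart threshold, and should be tied to the table

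*Protocol*

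**What the plan says.** The lead-in in Protocol 8.11.1 covers subjects whose QTcF rises above 480 msec on treatment (CTCAE Grade 2 or higher). It says they are to be evaluated for causality and "managed according to the following guidelines and" Table (8.11.1) 1. Four bullets follow, then the table.

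The third bullet opens with a condition, "If no other cause is identified and the Investigator believes it is appropriate, particularly if QTcF remains elevated", and then says "study treatment may be interrupted, and an ECG should be rechecked in approximately 1 week after the QTcF prolongation was first observed". On restart it says "If QTcF has recovered or improved and the Investigator believes it is safe to do so, re-challenge with study treatment should be considered" if treatment was held. It gives no msec value and no dose.

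The table's rows are specific:

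- Grade 2 (above 480 to 500 msec): "Interrupt ivosidenib Restart ivosidenib at 500 mg once daily after the QTc interval returns to less than or equal to 480 msec".
- Grade 3 (above 500 msec): "Interrupt ivosidenib. Resume ivosidenib at a reduced dose of 250 mg once daily when QTc interval returns to within 30 msec of baseline", or to 480 msec or less.
- Grade 4 (signs or symptoms of life-threatening arrhythmia): permanent discontinuation.

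No clause in the section says that the table prevails over the bullets.

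**The concern.** QT prolongation is the only important identified risk in Protocol 2.4 that applies to these subjects, because differentiation syndrome is listed there for hematologic malignancies only. Its management text should therefore state one rule. A site that works from the third bullet could depart from the table in two ways:

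- It could keep dosing at Grade 2 or 3 because another cause was found. This is a realistic case: exclusion criterion 28 and Section 6.3.2 allow QT-prolonging co-medication with monitoring.
- It could consider re-challenge while QTcF is still above the table's restart limit.

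Conflicting text also makes deviations hard to judge, since a site could act within the bullet and breach the table. What is at stake is subject safety and consistent conduct, not the efficacy result.

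**Working it through.** The plan states no figure here to reproduce, so the check is a comparison of texts plus simple threshold arithmetic.

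**Side by side (Protocol 8.11.1)**

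| Point | Third bullet | Table (8.11.1) 1 | Result |
|---|---|---|---|
| Interruption | Optional, on two conditions: no other cause found, and Investigator thinks it appropriate | Ordered without condition at Grades 2 and 3 | Conflict |
| Restart threshold | Recovered or improved, and Investigator thinks it safe | Grade 2: at most 480 msec. Grade 3: within 30 msec of baseline, or at most 480 msec | Conflict |
| Restart dose | None named | Grade 2: 500 mg. Grade 3: 250 mg | Silence, not conflict |
| Grade 4 | Within scope, since the lead-in covers Grade 2 and above | Permanent discontinuation | Bullet's scope too wide |

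On interruption the difference is more than tone. If a QT-prolonging co-medication is identified, the bullet's first condition fails and its permission to interrupt falls away, while the table still orders interruption. The Grade 3 row confirms this: an alternative etiology is only a reason to consider going back up to 500 mg after restart at 250 mg.

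**Restart limits**

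Inputs: the table's limits; baseline B, taken as the latest value before first dose (SAP 8.1.3).

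- Grade 2 limit = 480 msec.
- Grade 3 limit = max(480, B + 30), because the row joins its two criteria with 'or'.
- B = 420: max(480, 450) = 480.
- B = 450: max(480, 480) = 480.
- B = 460: max(480, 490) = 490.
- B = 470: max(480, 500) = 500.

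The Grade 3 limit is therefore 480 msec when the pre-dose baseline is 450 msec or less, and B + 30 above that.

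**Illustrations (assumed values, B at most 450 msec)**

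- Grade 3 event, 520 falling to 490: improvement 520 − 490 = 30 msec; distance above the limit 490 − 480 = 10 msec.
- Grade 2 event, 495 falling to 485: improvement 495 − 485 = 10 msec; distance above the limit 485 − 480 = 5 msec.

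Both readings satisfy the bullet's word for improvement, so re-challenge could be considered if the Investigator judged it safe. Both still lie in the table's band above 480 to 500 msec, so the table says to hold. The first example depends on the baseline: at B = 460 the Grade 3 limit is 490, and 490 msec would meet it.

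**The case against.** The strongest reply is that the two texts can be obeyed together. The lead-in joins them with 'and', and a permissive 'may' beside a mandatory row leaves one compliant course, which is to interrupt. Several pointers favour the table:

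- The lead-in names it.
- The footnote to Table (8.10.1.1) 1 cites it for QTcF dose modification.
- Its own asterisk note says that a rise of 60 msec or more "without value of QTc interval greater than 480 msec as per table above does not link to IMP dose interruption or reduction".
- The fourth bullet uses the same benchmark, though only for follow-up ECGs: "for 2 weeks following QTcF reduction ≤ 480 msec".

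This stands in large part. A careful site would follow the table, which limits the effect. It does not remove the fault: the bullets are given equal standing, no precedence is stated, and the bullet attaches conditions that the table does not have.

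The Sponsor safeguards also count, but only partly. Section 8.10.1.1 asks for discussion before dosing is delayed or modified; a decision not to interrupt is neither. The 24-hour reporting in Sections 8.6 and 8.11.1 is notification, not a dosing rule, and the Section 8.6 definition can be read as requiring arrhythmia signs.

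It may also be said that a subject restarted at 485 or 490 msec is still above 480 msec and returns to the Grade 2 row. That is so, but the same bullet applies again as well.

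Two stronger readings are tempting and not supported:

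- **That the texts contradict each other on dose.** They do not. The bullet names no dose, and the table fills the gap.
- **That 480 msec is the Grade 3 limit for everyone enrolled without Sponsor approval of a prolonged QTcF, because criterion 27 excludes 450 msec or more.** Baseline is the latest pre-dose value, and Table (4.1.2) 2 schedules a pre-dose ECG on C1D1. A subject at 445 msec at screening and 460 msec pre-dose (assumed values) would have a limit of 490 msec.

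**Conclusion.** The point holds as a harmonisation fault in a safety rule. The third bullet conflicts with Table (8.11.1) 1 on two points, interruption and restart threshold. It is silent on restart dose, and its scope literally reaches Grade 4. The table itself is complete; a reader might infer that the protocol lacks a rule for QTcF above 480 msec, and it does not.

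The effect is limited to sites that follow the general bullet instead of the grade-specific row. The 5 and 10 msec gaps are illustrations with assumed readings and a pre-dose baseline of 450 msec or less. The documents give no QT event rate, so no frequency can be stated. The sample size, the primary test and the other planned analyses do not depend on this text. The correction should be made because it is nearly costless and concerns the main identified risk in this population.

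**What to change.** Leave the table unchanged and replace the third bullet with text to this effect:

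> Interrupt, restart or permanently discontinue study treatment by grade as Table (8.11.1) 1 specifies. Recheck the ECG about 1 week after the prolongation was first seen, or more often if clinically needed. Restart only when the table's threshold is met and the Investigator judges it safe, at a dose no higher than the table gives. A subject already reduced to 250 mg stays at 250 mg unless the Sponsor approves re-escalation (Section 8.10.1.1).

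This keeps the Investigator's safety check and the start point of the ECG recheck. It deals with Grade 4 in line with Section 5.5.1, and it avoids an unintended return to 500 mg in a subject already reduced for another adverse event.

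The cost is a minor protocol amendment. No new clinical restriction is added: the discretion removed is already denied by the table, and the re-escalation condition is already in Section 8.10.1.1.
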